# Implementation of Antimicrobial Stewardship Directed PCT Testing and Treatment Algorithm

The antimicrobial stewardship team currently performs daily prospective audit and feedback for all patients admitted to VCH who receive antibiotics, providing in-person recommendations regarding antimicrobial modifications to providers as needed. This will continue in the standard of care arm. Current standard of care includes obtaining blood cultures, with or without CRP or other laboratory studies, and administering one or more broad spectrum antibiotics such as cefepime, piperacillin-tazobactam, and vancomycin for a minimum of 48 hours.

Prior to study initiation, the antimicrobial stewardship team will perform targeted education to ICU providers (attending physicians, residents and nurse practitioners) on the benefits and limitations of PCT use. A PCT-based algorithm to guide clinician decisions about antibiotic escalation or de-escalation will be disseminated to ICU providers (Fig. 1), displayed in ICU workrooms, and available on the intranet. PCT levels will be measured daily for the initial 3 days following randomization and then at day 5 post-randomization. Subjects in the intervention group will have a stewardship provider ([name]) review their records daily and make in person rounds in the ICU to strongly encourage provider adherence to the PCT testing and algorithm-based management. De-escalation of antibiotics will be recommended if the PCT level falls by 80% or more of the peak PCT level, or when the PCT level is less than or equal to 0.25  $\mu$ g/L (Fig. 1). Continuation or escalation of antibiotics will be recommended if PCT level is greater than or equal to 0.5  $\mu$ g/L, or increased as compared to previous peak PCT level. These levels are comparable to those used in previously cited studies.

#### **Laboratory Analysis**

The Roche Procalcitonin test is a diagnostic test that is FDA approved for use in adults and has been approved by the VUMC laboratory formulary committee. It will be available for routine clinical use across the medical center, including in children at VCH in the near future. Although the Roche PCT test is not approved for use in children, the same test manufactured by Biomerieux does not have an age restriction on its FDA approval. This study is not intended to support approval of the test in children, nor promote non-approved indications. In this study we will use the Roche PCT test in an off-label population (children), but it will be used within the scope of clinical practice at Vanderbilt, following VUMC-approved guidance. A group of ICU, ED, and ID physicians and the chemistry lab director were involved in developing the strategy for reporting PCT results in the VUMC electronic medical record. The planned test reporting comments and PCT threshold interpretations are more conservative than used in some studies (Fig. 1) and are shown below:

Procalcitonin can help differentiate viral from bacterial respiratory infection. Procalcitonin may be used to guide antibiotic de-escalation in sepsis (when compared to admission level):

PCT < 0.1 ng/ml Bacterial infection very unlikely

PCT 0.1 to 0.25 ng/ml Bacterial infection unlikely

PCT 0.25 to 0.5 ng/ml Bacterial infection possible

PCT > 0.5 ng/ml Increased probability of bacterial infection, encourage antibiotic therapy

Serum PCT levels will be determined daily per VCH Laboratory protocol, using the Elecsys BRAHMS PCT test. The required blood volume is 0.5 - 1 mL and the estimated turnaround-time for the test is 3 hours or less. We will apply for a waiver of consent for the first blood sample, so that patients admitted to the ICU who are started on IV antibiotics will have leftover blood that is obtained during routine clinical care stored in a study refrigerator until study consent is obtained. For subjects enrolled in the intervention arm, PCT levels will be monitored at study enrollment, every 24 hours for the initial 2 days following randomization, and then at day 5 post-randomization. Whenever possible, leftover serum, from clinically collected specimens, will be used for PCT testing. For subjects in both arms, CRP, white blood cell count, and other relevant laboratory tests that are obtained for routine clinical care will be abstracted from the medical record.

#### **Study Outcomes**

The **primary outcome** is days of antibiotic therapy in the first 14 days following randomization. **Secondary outcomes** are duration of broad-spectrum antibiotic therapy (defined as vancomycin, daptomycin, amikacin, ceftazidime, cefepime, piperacillin/tazobactam, aztreonam, carbapenems), time from randomization to first appropriate antibiotic modification (escalation or de-escalation), 30-day mortality, reinitiation of antibiotics for a bacterial infection within 30-days of antibiotic discontinuation, length of ICU stay, length of overall hospital stay, ventilator days, rates of antibiotic-

associated complications (i.e. rash, neutropenia, thrombocytopenia, acute kidney injury [defined as increase in serum creatinine  $\geq 0.3$  mg per dL or  $\geq 1.5$ -fold from baseline, or urine output < 0.5 mL per kg per hour for more than six hours], hepatotoxicity [defined as > 2-fold increase in alanine aminotransferase, ALT, or conjugated bilirubin], or *C. difficile* infection), infection with multi-drug resistant organisms (defined as methicillin-resistant *S. aureus*, vancomycin-resistant *Enterococcus*, 3rd generation cephalosporin non-susceptible *Enterobacteriaceae*, multi-drug resistant *Pseudomonas aeruginosa* [resistant to aminoglycosides, cephalosporins, floroquinolones and carbepenems], carbepenem-resistant *Acinetobacter*, and *Candida* spp obtained from otherwise sterile sites [i.e. blood or urine cultures]), cost of antibiotics from hospital billing data, and adherence to the PCT-guided algorithm.

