# **Specific Aims**

- 1. Compare antimicrobial utilization among children in the ICU who receive standard-of-care testing plus stewardship vs. PCT-based treatment plus stewardship. We will compare days of antibiotic therapy in the first 14 days following randomization between the study arms. We will test the hypothesis that duration of antibiotic therapy will be 2 days shorter in the group with PCT-guided management vs. the group with standard of care testing and treatment.
- 2. Compare clinical outcomes and safety among children in the ICU who receive standard-of-care testing plus stewardship vs. PCTbased treatment plus stewardship. We will compare mortality, length of stay, recurrence of infection, and antibiotic-associated adverse events (rash, myelosuppression, renal impairment, hepatotoxicity, *C. difficile* infection) between the study arms. We will test the hypothesis that outcomes and safety will be comparable between the study arms.

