#### **Study Timeline**

The VUMC clinical laboratory PCT validation is complete. This protocol has been approved by the VUMC IRB. Provider education, and PCT clinical algorithm development is complete. We estimate that we will attain the target sample size within 16 months. Data analysis and abstract and manuscript preparation will be completed in the year after the study closes.

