### 7.0 Risks

Risks include those associated with routine blood draws – pain, redness, soreness, bruising, or infection may occur at the needle stick site. Rarely some people faint. We plan to offer EMLA cream to subjects prior to blood draws. A maximum of 4 blood draws will be obtained for procalcitonin testing in patients randomized to the intervention arm. Whenever possible, for PCT testing, we will use leftover blood from routine laboratory testing performed as part of ICU care.

Because PCT has not been well studied for making antibiotic modification decisions in children, there may be the risk of premature cessation of antibiotics. However, to prevent this from happening, all decisions to stop or continue antibiotic therapy will be made by the ICU attending physician, based on clinical judgement and standard of care studies such as bacterial cultures, WBC,CRP, and radiographic evaluations

The decision to start antibiotic treatment will in no way be affected by the study. In all subjects antibiotics will be started based on clinical suspicion of infection or microbiologic evidence of infection. This decision is at the discretion of the treating intensive care physician. Similarly, the decision to obtain PCT testing and/or adhere to the PCT algorithm or stewardship recommendations will be at the discretion of the ICU attending physician.

All subjects in both arms will have baseline audit of antimicrobial orders with feedback to providers by the antimicrobial stewardship team. For subjects in the intervention arm, the stewardship team will additionally recommend PCT testing and treatment, with recommendations to initiate or expand antibiotic use at PCT levels > 0.5 ug/L and to stop antibiotics when PCT levels decrease by >80% from peak concentration or to an absolute value < 0.25 ug/L.

Multiple studies to date have demonstrated that procalcitonin-guided antibiotic de-escalation algorithms are as safe as standard of care management in the adult ICU setting. As such, we do not anticipate increased risk of infection relapse rates or

increase in 30-day mortality between groups. These parameters will be monitored throughout the study and adverse events will be recorded and reported as detailed below.

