#### 12.0 Follow-up and Record Retention

The projected duration of the study is from the time of IRB approval through June 30, 2019.

Data will be stored in a password-protected RedCap database. Paper copies of the data will be kept to the absolute minimum. Only the PI and co-investigators will have access to the master patient key and patient identifiers during the study collection period. After the collection period, only the PI will maintain the master patient key for future study that may require linking clinical laboratory values with clinical data. The key will be maintained in the PI's office in the Section of Infectious Diseases at VUMC on a single password-protected hospital computer. Any paper copies or data on paper will be stored in a locked filing cabinet in the PI's office. Paper copies will be destroyed at the earliest possible time by being discarded in the hospital HIPAA-approved receptacles for PHI to be shredded according to hospital policy.

The PI, co-investigators and laboratory personnel will be appropriately trained to maintain the confidentiality and protection of PHI according to the study design and hospital practice.

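### The SAP has no analysis of antibiotic reinitiation or recurrence of infection, which the protocol lists as a safety comparison between the arms

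*Protocol*

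**What the plan says.** The protocol commits to this outcome in three places.

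- **Specific Aims, Aim 2:** "We will compare mortality, length of stay, recurrence of infection, and antibiotic-associated adverse events". The stated hypothesis is "We will test the hypothesis that outcomes and safety will be comparable between the study arms".
- **Study Outcomes (section 6.0):** the secondary outcomes include "reinitiation of antibiotics for a bacterial infection within 30-days of antibiotic discontinuation".
- **Section 7.0, Risks:** the protocol accepts that "there may be the risk of premature cessation of antibiotics". It then says "we do not anticipate increased risk of infection relapse rates", mentions 30-day mortality in the same sentence, and adds "These parameters will be monitored throughout the study".

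The SAP, dated June 4, 2019, presents itself as the statement of the planned analyses. Its clinical outcome measures, numbered 1 to 7 without a gap, are in-hospital death, hospital stay, ICU days, days of invasive ventilation, antibiotic-associated complications, new hospital-acquired infection or resistant organism, and re-admission. The interim look in section D, which is there for safety, compares baseline characteristics, days of therapy (DOT), 30-day mortality and ICU stay. Reinitiation, recurrence and relapse appear nowhere in the SAP.

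**The concern.** The trial asks whether antibiotics can be cut back early without harm. Its main measure rewards stopping. Reinitiation is the only protocol outcome whose clock starts when antibiotics stop, so it is closely tied to the risk of stopping too soon that section 7.0 describes. Without it, the trial could report shorter courses and have no planned between-arm result on whether treatment had to be resumed more often. This is a conflict between the protocol and the SAP on a promised safety comparison, and not just a missing detail.

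**Working it through.** The omission involves no stated figure, so there is none to reproduce. The check matches the two documents item by item and then works out the time windows.

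**1. Protocol secondary outcomes against the SAP.** Study Outcomes lists 11: broad-spectrum duration, time to first modification, 30-day mortality, reinitiation, ICU stay, hospital stay, ventilator days, antibiotic complications, resistant-organism infection, antibiotic cost, and algorithm adherence. Nine have a SAP counterpart; reinitiation and cost do not (11 − 9 = 2). Cost is not a safety outcome.

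**2. The nearest SAP items.**

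| SAP item | What it misses |
|---|---|
| Re-admission within 30 days | Any cause; misses re-treatment without re-admission |
| New hospital-acquired infection or resistant organism | Index stay only; new infection, not relapse |
| DOT to day 14 | Adds restarted days up to day 14 but does not identify a restart |
| Escalation tables | The escalation definition includes adding a drug, so restarts mix with additions in patients still on treatment |
| Time to first appropriate modification | Stopping counts as a de-escalation, so a restart after an appropriate stop is not counted |
| Time-to-cessation model | No rule for a restart |

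**3. DOT horizon against the 30-day window.** For a stop on day *s* after randomization, DOT overlaps (14 − *s*)/30 of the protocol's window:

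- *s* = 0: 14/30 = 47%
- *s* = 2: 12/30 = 40%
- *s* = 7: 7/30 = 23%
- *s* = 14: 0/30 = 0%

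The stop days are examples. These are shares of calendar time only.

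Two one-drug illustrations show that DOT can move either way:

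- Two days of treatment with a restart on day 15 scores DOT 2. Four uninterrupted days scores DOT 4. The restarted patient looks 2 days better, which equals the hypothesised effect.
- Two days of treatment with a 3-day restart from day 5 scores 2 + 3 = 5, which is worse than 4.

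**4. Follow-up.** The window ends on day *s* + 30: day 32 for *s* = 2, day 37 for *s* = 7, day 44 for *s* = 14. The SAP's DURATION line stops at discharge, or at day 30 for those still in hospital. The protocol states: "The projected duration of the study is from the time of IRB approval through June 30, 2019". A patient randomized on that last day who stops on day 14 has a window ending 44 days later, on August 13, 2019. The SAP's antibiotic tables expect some courses beyond day 14, and those windows end later still. Study Timeline says: "Data analysis and abstract and manuscript preparation will be completed in the year after the study closes".

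**5. What a difference test can show about comparability.** SAP section F plans a Pearson chi-squared test for categorical outcomes and no interval for a between-arm difference. Assume 140 per arm (an equal split of 280), a common event rate *p*, and no clustering. The 95% half-width for a risk difference is 1.96 × √(2*p*(1 − *p*)/140):

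- *p* = 3%: 4.0 points
- *p* = 5%: 5.1 points
- *p* = 10%: 7.0 points

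Power to detect a doubling from *p*₁ to *p*₂, with mean rate *p̄*, is Φ[(*p*₂ − *p*₁ − 1.96√(2*p̄*(1 − *p̄*)/140)) / √((*p*₁(1 − *p*₁) + *p*₂(1 − *p*₂))/140)]. For 5% to 10% this is Φ[(0.0500 − 0.0617)/0.0313] = 35%. For 10% to 20% it is Φ[(0.1000 − 0.0836)/0.0423] = 65%. The rates are assumptions, since the documents give none. The SAP describes a cluster crossover design, so these figures are illustrative only.

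**The case against.** **Premature cessation is already watched.** Protocol section 8.0 treats harm from a PCT-led early stop as an adverse device event, recorded in the study database and reported in an expedited way. Section 7.0 points forward to that reporting. This stands as surveillance, and a reader might infer from the SAP alone that nobody is looking, which would be wrong. But it relies on case-by-case attribution by the investigator or treating providers and concerns harm from a PCT result. It is not a comparison of re-treatment between arms.

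**Other safety outcomes remain.** Mortality, re-admission, complications and new infections are all compared. That is correct, and safety is not left unassessed. They are partial proxies for a restart.

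**DOT penalises restarts.** It does, up to day 14. A reader might infer that restarts go uncounted; the documents do not support that. They are added to exposure without being identified.

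**The protocol's clock is not ideal.** Discontinuation happens after randomization and is what the intervention is meant to change, so a window that starts there does not compare arms from a common origin. This is a fair point. It argues for a second version timed from randomization, and not for leaving the outcome out.

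**Conclusion.** The omission is established by the text: Aim 2 and the secondary outcome list promise the comparison, section 7.0 promises monitoring of relapse, and the SAP provides for none of the analysis. It should be corrected. One of 11 secondary outcomes is affected in this way, and it is the only safety outcome without a counterpart.

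The effect on the trial's conclusions cannot be sized, because neither document gives a restart rate. A reader might take the 47% to 0% overlaps as the share of restarts DOT would capture. That would require restarts to be spread evenly over the 30 days, which nothing in the documents supports.

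The point about intervals follows from the hypothesis of comparable safety. A non-significant chi-squared result would not establish it, and the half-widths of about 4 to 7 points depend on the assumed rates, equal arms and no clustering.

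Mortality wording is a minor, separate matter. The SAP's outcome measure is limited to in-hospital death, while its objectives, interim section and tables, and the protocol, give 30-day death without that limit. This may be shorthand and should not be read as a planned exclusion of later deaths.

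**What to change.** 1. Restore reinitiation/recurrence as a SAP clinical/safety outcome with the protocol's definition and its own by-arm table.
2. State what counts as discontinuation and as a restart for bacterial infection. Keep patients who die first or never stop in the denominator, as separate categories.
3. Also report the outcome over a fixed window from randomization, with the end day stated in advance.
4. Ascertain it by record review to the end of each patient's window, and extend the DURATION line to match.
5. Report this and the other binary safety outcomes as between-arm differences with 95% confidence intervals, and say that a non-significant test will not be read as comparability.
6. Separately, use one mortality wording throughout the SAP.

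Adding the outcome to the interim look is probably moot: that look falls at 50% of accrual, and the SAP is dated 26 days before the projected study end (June 4 to June 30, 2019).

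The cost is SAP wording, one outcome table with its fixed-window version, and post-discharge chart review for up to 280 participants. Part of that review is already needed for 30-day re-admission. Some windows close after June 30, 2019, and after August 13 for courses beyond day 14, but the year allowed for analysis leaves room. Re-treatment at other hospitals may be missed, and the SAP should say so.

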#### **Study Timeline**

The VUMC clinical laboratory PCT validation is complete. This protocol has been approved by the VUMC IRB. Provider education, and PCT clinical algorithm development is complete. We estimate that we will attain the target sample size within 16 months. Data analysis and abstract and manuscript preparation will be completed in the year after the study closes.

### 7.0 Risks

Risks include those associated with routine blood draws – pain, redness, soreness, bruising, or infection may occur at the needle stick site. Rarely some people faint. We plan to offer EMLA cream to subjects prior to blood draws. A maximum of 4 blood draws will be obtained for procalcitonin testing in patients randomized to the intervention arm. Whenever possible, for PCT testing, we will use leftover blood from routine laboratory testing performed as part of ICU care.

Because PCT has not been well studied for making antibiotic modification decisions in children, there may be the risk of premature cessation of antibiotics. However, to prevent this from happening, all decisions to stop or continue antibiotic therapy will be made by the ICU attending physician, based on clinical judgement and standard of care studies such as bacterial cultures, WBC,CRP, and radiographic evaluations

The decision to start antibiotic treatment will in no way be affected by the study. In all subjects antibiotics will be started based on clinical suspicion of infection or microbiologic evidence of infection. This decision is at the discretion of the treating intensive care physician. Similarly, the decision to obtain PCT testing and/or adhere to the PCT algorithm or stewardship recommendations will be at the discretion of the ICU attending physician.

All subjects in both arms will have baseline audit of antimicrobial orders with feedback to providers by the antimicrobial stewardship team. For subjects in the intervention arm, the stewardship team will additionally recommend PCT testing and treatment, with recommendations to initiate or expand antibiotic use at PCT levels > 0.5 ug/L and to stop antibiotics when PCT levels decrease by >80% from peak concentration or to an absolute value < 0.25 ug/L.

Multiple studies to date have demonstrated that procalcitonin-guided antibiotic de-escalation algorithms are as safe as standard of care management in the adult ICU setting. As such, we do not anticipate increased risk of infection relapse rates or

increase in 30-day mortality between groups. These parameters will be monitored throughout the study and adverse events will be recorded and reported as detailed below.

# 8.0 Reporting of Adverse Events or Unanticipated Problems involving Risk to Participants or Others

Clinical adverse events will be monitored and recorded throughout the study. Serious adverse events include death, or other life-threatening complications like hemorrhage. Adverse drug/device events include if the PCT test result leads to premature cessation or de-escalation of antibiotics and causes harm to the patient, as determined by the PI or treating providers. Serious adverse device events include if PCT test results lead to premature antibiotic cessation, resulting in death, as determined by the PI or treating providers. All adverse events, adverse drug events, serious adverse events, and serious adverse drug events will be recorded by the study team in the RedCap data collection form and reported in an expedited manner to Roche, the VUMC IRB (in accordance with the Vanderbilt IRB Procedure III.L.1 – v.17. ) and the FDA as required.

# 9.0 Study Withdrawal/Discontinuation

Subjects can withdraw from the study at any time.

# **10.0 Statistical Considerations**

Based on data from studies evaluating PCT use among adult ICU patients, we estimate that median consumption of antibiotics will be 2.0 days less in the PCT group as compared to the control group. Assuming normal distribution, and a standard deviation of 6 days, a sample size of 125 patients per arm will provide at least 80% power to detect a difference in antibiotic duration of at least 2.0 days between study arms. These calculations are based on a chi-squared test with a two-sided Type 1 error rate of 0.05. Per clinical pharmacy data, the average duration of an antibiotic course per patient in VCH ICUs is 4 days, thus a difference of 2.0 days would be clinically significant.

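### Section 10.0's power of at least 80% does not follow from its own inputs, which give about 75% at 125 per arm, and its normal distribution with SD 6 is unsourced and fits a short count of days poorly

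*Protocol*

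**What the plan says.** Protocol section 10.0 takes its effect size from earlier studies: "we estimate that median consumption of antibiotics will be 2.0 days less in the PCT group as compared to the control group". The sizing statement itself reads: "Assuming normal distribution, and a standard deviation of 6 days, a sample size of 125 patients per arm will provide at least 80% power". The gap that this power refers to is 2.0 days of antibiotic duration. The test named for the calculation is "a chi-squared test with a two-sided Type 1 error rate of 0.05". To argue that 2.0 days matters clinically, the section adds that "the average duration of an antibiotic course per patient in VCH ICUs is 4 days". No source is given for the SD, no arm means are stated, and no allowance for dropout appears.

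The protocol's Study Outcomes section defines the primary outcome as "days of antibiotic therapy in the first 14 days following randomization". The SAP makes it days of therapy (DOT) per patient within 14 days. Its Antibiotic Use section caps this at 14 days for each antibiotic, so a child on two drugs can total more than 14. The SAP's Analysis Plan makes the primary test a Wilcoxon rank-sum test that does not assume normality. The SAP's sample size is 280, against 250 (2 × 125) in the protocol.

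**The concern.** There are two separate faults.

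The first is arithmetic. All the inputs for a comparison of two means are printed (difference, SD, number per arm, alpha, sidedness), and they do not return the printed power. No outside assumption is needed to see this.

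The second is about the inputs. An SD of 6 days is large for an outcome counted over 14 days in units where the average course is 4 days. A normal distribution with that SD puts a sizeable share of children at negative durations. The SAP itself drops normality for the primary test, but the sizing was never restated to match.

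At stake is what the trial may claim it was designed to detect. Readers will use the planned power and detectable difference as context for a null result. Measured against a 4-day average, a design sensitive to about 2.1 days is quite different from one sensitive to about 1.4 days.

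**Working it through.** **Inputs.** Difference δ = 2.0 days, SD σ = 6 days, n = 125 per arm, two-sided α = 0.05 (all from Protocol section 10.0); total 280, taken as 140 per arm (SAP; 1:1 is assumed). Patients are treated as independent. The section names a chi-squared test, but it gives no proportions, so the check uses the two-sample comparison of means that its inputs describe.

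**Reproducing the printed power.** Power = Φ(δ / (σ√(2/n)) − 1.960).
- n = 125: 2 / (6 × 0.1265) = 2.635; Φ(2.635 − 1.960) = Φ(0.675) = **75.0%** (t-test 74.7%).
- n = 140: 2 / (6 × 0.1195) = 2.789; Φ(0.829) = **79.6%** (t-test 79.4%).

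**Number needed for 80%.** n = 2(1.960 + 0.842)²σ²/δ² = 2 × 7.849 × 36 / 4 = 141.3, so **142 per arm** (143 by t-test). With the usual 3/π efficiency of the Wilcoxon test under normality, 142 / 0.955 gives about 149.

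**Detectable difference at 125 per arm, 80% power.** 2.802 × 6 × 0.1265 = **2.13 days**. For 125 per arm to give 80% at 2.0 days, the SD would have to be 5.64.

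**Could other settings explain 125?** A one-sided test gives 83.9% power and needs 112 per arm, which becomes 125 with 10% dropout. But the section says two-sided and states no dropout, so this is only a guess at the figure's origin.

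**Does SD 6 fit the outcome?** A variable confined to 0–C with mean m has SD at most √(m(C − m)).

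| Reading | Mean | Cap | Largest SD |
|---|---|---|---|
| Calendar days, mean equal to the local course average | 4 | 14 | √40 = 6.32 |
| Calendar days, 2 days lower | 2 | 14 | √24 = 4.90 |
| Durations in the adult ICU trial described in Protocol section 3.0 | 7 and 5 | 14 | √49 = 7.00 and √45 = 6.71 |
| DOT, two antibiotics | 2 | 28 | √52 = 7.21 |

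The means of 4 and 2 are an assumption. The 4 is a hospital average per course, and the 2 subtracts a difference in medians from it. At those means the normal tails below zero are Φ(−4/6) = 25% and Φ(−2/6) = 37%. At means of 7 and 5, SD 6 is attainable, but the normal still puts 24% and 27% of values outside 0–14.

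**Which way does the power move?**
- Mean difference kept at 2.0 days, smaller common SD (assumed), 125 per arm: 88% at SD 5 and 98% at SD 4. The detectable differences are 1.77 and 1.42 days.
- The largest possible SDs at means 4 and 2 on 0–14 (pooled √((40 + 24)/2) = 5.66): 79.8%.
- Simulated bounded outcomes with means 4 and 2: Wilcoxon power 92% with SDs 6 and 4.8, and 98.7% with SDs 5 and 4.
- The stated normals clipped to 0–14 (means 4 and 2 before clipping): the mean difference shrinks to 1.3 days, and Wilcoxon power is about 69% at 125 and 75% at 140 per arm.

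The answer depends on the distribution assumed, and the documents do not supply one.

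**The case against.** The strongest reply is that a generous SD is the safe side on which to err. If the true SD is below 6 and the mean difference really is 2.0 days, 125 per arm has more power than SD 6 implies, and at SD 5 or less it clears 80% comfortably. That stands. The one low figure, 69%, comes from clipping a normal that fits poorly to begin with, and clipping also shrinks the assumed effect. It shows sensitivity to the assumption and is not an estimate of the trial's power.

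A reader might also infer that SD 6 is mathematically impossible for this endpoint. The documents do not support that. The protocol states no arm means, and the 4-day figure is not labelled as the control-arm mean of the 14-day outcome. Means of 7 and 5 allow SD 6 on a 0–14 scale. The SAP's cap per antibiotic lets total DOT exceed 14, and at a mean of 2 any cap of 20 or more allows SD 6 (2 + 36/2 = 20).

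Finally, the SAP's Wilcoxon test protects the validity of the primary analysis whatever the planning SD was, and what a null result excludes will depend mainly on the observed data. Both points are right. They limit the consequence, but they leave the printed power wrong and the SD unsupported.

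**Conclusion.** The point holds in two parts.

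First, the printed power is wrong on the protocol's own inputs: about 75% rather than at least 80% at 125 per arm, a shortfall of about 5 points. The detectable difference at 80% power is 2.13 days rather than 2.0. The SAP's 280 comes close to the target, at about 79%. This part rests only on printed figures, on the comparison of means that they describe, and on 1:1 allocation for the 280.

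Second, the normal distribution with SD 6 has no stated basis and fits poorly with a bounded, non-negative count of days. How poorly depends on arm means that the protocol does not give.

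It would be tempting to conclude that the trial is underpowered. That does not follow: if the true SD is smaller and the effect is as assumed, power rises, and the direction of the overall error is not established. The cluster crossover design named in the SAP is not modelled here, because the documents give neither an intracluster correlation nor a number of periods.

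**What to change.** Leave enrolment unchanged. In Protocol section 10.0:

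1. Replace the power claim with what the stated inputs give: about 75% at 125 per arm, or about 79% at 140. Say which sample size applies, since the protocol implies 250 and the SAP says 280.
2. Replace the normal, SD 6 basis, and the reference to a chi-squared test, with power and the 80%-power detectable difference for the planned Wilcoxon test on DOT as the SAP defines it.
3. Take the distribution from the clinical pharmacy data behind the 4-day average if patient-level values can be had. The protocol reports only the average, so this cannot be presumed. Otherwise show the results over a stated range of SDs and label them as assumptions.

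The cost is one recalculation or short simulation and a rewritten paragraph. No procedure changes, and the restated power may come out higher or lower than 80%.
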